Evaluating Detection of SARS-CoV-2 antibodies using home test kits (EDSAB-HOME study)

Protocol 30.05.2020 Version 04.03

assume that the accuracy of self-read tests as assessed against expert-read tests is independent of the true antibody status.

In the first analysis, we will examine the probability of a self-read positive result among expert positive results, and the probability of ("false") self-read positive result among expert negatives, both as functions of reported exposure and illness experience, using logistic regression.

The second analysis will estimate the overall Sensitivity of the self-read HTK as Pr(self-read +ve|Expert +ve) x Sensitivity of the Expert-read POC based on the evidence synthesis results (Objective 1, Analysis 2). Similarly the overall specificity of the self-read POC will be estimated as: Pr(self-read -ve|Expert -ve) x Specificity of the Expert-read HTK based on the evidence synthesis results.

Objective 3

To assess whether home photographic recording of HTK is feasible and enhances accuracy of recording relative to user reading;

If possible, we will also compare to results from an automated pixel analysis of a photograph of the test taken by the person tested, and a visual analysis of a photograph taken under optimal conditions in the field. We will report concordance between the methods of interpreting results, and characteristics of discordant results (including whether they are positive or negative using the HPA test).

Objective 4

To determine the acceptability of the tests to the population;

Data (including both quantitative and free text) obtained from the baseline questionnaire on acceptability and usability of the HTK programme completed by participants will be summarised by counts, descriptive statistics and pseudo-anonymised quotes. In addition, work conducted by user researcher team at NHSX and qualitative interviews conducted prior and during the pilot phase of the programme will be included into the results of the evaluation, where appropriate/necessary.

Objective 5

To inform the instructions and other advice to be provided to people undertaking the tests and to those who have a positive and a negative result;

Results obtained on the sensitivity and specificity of the HTK will inform what advice should be given, including whether confirmatory testing using laboratory based tests will be necessary for any subsets of the population, including healthcare workers.

Objective 6

To describe the numbers of coronavirus responsive T cells in peripheral blood of subjects using ELISPOT technology, and its relationship to serological tests for SARS-CoV-2, and to clinical risk factors for COVID-19;

Evaluating Detection of SARS-CoV-2 antibodies using home test kits (EDSAB-HOME study)

Protocol 30.05.2020 Version 04.03

We will analyse the number of coronavirus responsive T cells, as determined by T-SPOT Coronavirus, as a continuous variable, describing its relationship with age, gender, ethnic group, occupation, recent symptoms and previous exposure to SARS-CoV-2 assessed using symptoms and previous positive tests, as well as with enzyme immunoassay results. Some of these data may be useful as part of a regulatory package applying for regulatory approval of T-SPOT coronavirus tests for clinical use. Discussions as to the appropriate analysis of this data are ongoing between Oxford Immunotec Ltd and MHRA. An appendix pre-specifying these analyses will be added to this protocol when these discussions are complete.

Objective 7

To provide estimates of the hazard of development of COVID-19 compatible symptoms, or of COVID-19 related hospitalisation, among individuals with a positive vs negative laboratory and HTK antibody test kit results, and its relationship to SARS-CoV-2 responsive T cells from the T-SPOT Coronavirus test;

Development of COVID-19 compatible symptoms will be assessed through the weekly follow-up text or email messages. Development to COVID-19 related hospitalisation will be assessed through data linkage to routine laboratory and hospital record systems (SGSS and HES). These will be exploratory end-points, with the acknowledgment that we may be underpowered to detect the rarer, severe endpoints (e.g. hospitalisation) within our current cohort. However, this step aims to assess the feasibility of the process, and may lead to a secondary follow up study (e.g. linkage of the first 50,000 who use this service to laboratory and hospital records) to estimate the rate of development to COVID-19 related hospitalisations, if operationally feasible.

Descriptive statistics, frequency and percentages (life tables) will be used to describe outcomes, split by exposure type. Exposure of primary interest will be considered HTK result (positive or negative), laboratory based EIA result, and SARS-CoV-2 responsive T cell numbers, determined by T-SPOT Coronavirus assays, and outcome will be considered either COVID-19 compatible symptoms and/or progression to severe COVID-19 disease, as defined operationally by hospitalisation.

Secondary exposures of interest will include age, sex, exposure to known confirmed case, occupation, behaviour (i.e. at work or self-isolation), co-morbidities, and other risk factors. We will model the hazard of a COVID-19 related outcome (symptoms, hospitalisation) over time accounting for subject factors as covariates, using generalised linear mixed models and cure-rate type time-to-event models accounting for time-varying covariates.

Objective 8

To provide a panel of plasma which can be used for proficiency testing and batch release assay.

Plasma will be stored in PHE for this purpose. We will work to bank these materials in an NIHR Biorepository.

Other considerations

Safety Considerations

There is little risk to the subjects. A trained phlebotomist or research nurse will collect up to 20ml of blood from individuals, which is a small volume (about 5% of the amount donated at blood donation). Some

Evaluating Detection of SARS-CoV-2 antibodies using home test kits (EDSAB-HOME study)

Protocol 30.05.2020 Version 04.03

people may feel faint when they give blood, but this is transient and is not harmful. Some bruising may occur where the blood is taken, but this is also transient and harmless. All benefits are indirect, and will inform the programme's implementation and subsequent public health advice.

Benefits of taking part

Participants will receive the results from the laboratory-based tests, if they wish to do so. If they take part in stage two, they will have access to HTK results indicating whether they have antibodies against COVID-19. The volunteers contribute to the development and evaluation of the SARS-CoV-2 antibody testing programme.

Dissemination of Results and Publication Policy

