- 7. An estimate of the hazard of development to COVID-19 compatible symptoms, or COVID-19 related hospitalisation, among individuals with a positive vs negative laboratory and HTK anti-coronavirus antibody results, alone and in combination with SARS-CoV-2 responsive T cell numbers;
- 8. A panel of plasma which can be used to evaluate the accuracy of any next-generation immunochromatographic kits in a 'bridging' validation / verification study, for quality assurance, and lot qualification.

Study Design

Methods: Test evaluation, including a prospective cohort study of high risk (healthcare workers) and lower risk (e.g. police) populations for COVID-19.

Population: The test evaluation population will reflect the population projected to use the home testing service in the initial stages of HM Government test rollout, which is likely to be front line workers such as healthcare staff and police/fire/rescue officers. A representative sample from a group of organisations will be recruited if possible.

Subsequently, testing may be extended to the general public, once the first two target groups have been studied.

In addition, a selection of individuals with previous positive SARS-CoV-2 tests ("known positives") from OLS-WS-2 (Antigen testing) (at least 2 weeks after initial infection) may be included into the population.

Evaluating Detection of SARS-CoV-2 antibodies using home test kits (EDSAB-HOME study)

Protocol 30.05.2020 Version 04.03

Inclusion criteria:

- Currently working at their place of work;
- Aged 18 years or older;
- Able to read and English, so as to understand the protocol;
- Has an in-use personal email address and mobile phone.

Exclusion criteria:

- Is currently experiencing COVID-19 compatible symptoms.
- Has experienced COVID-19 compatible symptoms in the last seven days;
- Meets definition of "exceptionally vulnerable" on medical grounds, including immunosuppression, previous oncological treatments these people should not be at work anyway;
- Unable to read normal sized print with glasses;
- Taking part in vaccine studies.

Methodology

Recruitment:

PHE will aim to recruit initial users of the HTK program, with the overall aim of obtaining a representative sample of initial intended users. This will comprise of three key cohorts, with different expected prevalence, allowing some exploration of whether sensitivity may vary by severity:

- Healthcare workers (1,500 persons). All individuals working on site will be eligible to enrol.

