- Police workers (1,000 persons) [or other cohort of non-healthcare workers]. All individuals working on site will be eligible to enrol.
- General population, the recruitment of which will be considered at a later date once the first two groups have been studied.

Additionally, a fourth cohort will be approached. These are individuals who have previous tested positive as part of health care worker screening, and whose details are known to the NHS Business Services Authority (NHSBSA). The DHSC has undertaken legal review, and has confirmed to us that their processing of the personal details of these individuals for this purpose is lawful, and that they are prepared to send a communication to them on our behalf. We will attempt to recruit up to 500 such workers.

Recruitment strategy: Workplace based recruitment

Senior leadership (CEO or equivalent) from selected workplaces will be sent a letter signed by senior leadership in DHSC inviting their institution to take part in the study and their specific ask for taking part. They will have the opportunity to have a phone call with senior leadership in DHSC to discuss the proposed processes and answer any questions they may have.

If they agree to take part, they will be sent a template email to send out to their employees. This will include information on the criteria for taking part, the participant information sheet, and links to the consent form, online questionnaire, and appointment booking system. They will also be sent a template poster which can be put up in their place of work. This will emphasise to their staff that the study is voluntary, and they have no obligation to take part. Depending on recruitment rates, we may restrict recruitment to a convenience sample of the first 100-150 people to book an appointment per institution. Additional, walk in slots may be available, depending on logistical capacity.

Evaluating Detection of SARS-CoV-2 antibodies using home test kits (EDSAB-HOME study)

Protocol 30.05.2020 Version 04.03

Recruitment strategy: Workplace based recruitment

DHSC, in collaboration with the NHSBSA, will send a closely related template email to that sent out by NHS Trusts to individuals who have previously tested positive.

Three stages:

The study will take place in three stages (Figure 1):

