 The anticipated initial users of the service (including up to 500 "known positives") are recruited (2,500 persons) prior to the HTKs becoming available, and invited to attend a community testing centre on specific day(s). At the centres, metadata will be collected on all individuals (in the form of an electronic questionnaire) and a venous blood sample taken.

In a small number (n ~ 100) of individuals, a capillary blood sample and dried blood spot (DBS) will be taken. This will allow assay optimisation for enzyme immunoassays which may in future use capillary blood samples.

The blood samples will be tested with one or more commercial EIAs. These include products by EuroImmun (anti-Spike) Roche (anti-N) Abbott (anti-N).

Emerging data indicates that anti-N assays have very good performance, with enhanced sensitivity relative to anti-S assays. For all the assays, sensitivity, particularly early in disease and in cases of asymptomatic infection, is less well characterised.

We will use a single assay with the highest published performance available, which we will refer to as the High Performance Assay (HPA). We envisage this will be one of the two available anti-N EIAs. Subject to availability, we will perform both an anti-S and anti-N assay on all samples as well, but the initial analysis of the HTK will be against the HPA. Other experimental assays under development by the DHSC project or PHE may also be used. A plasma bank will be set up, ready to be tested with the HTK in the laboratory once available. The clinical performance of the HTK will be estimated in two separate analyses (1) assuming the HPA is 100% sensitive and specific (which may, however, be incorrect); and (2) Bayesian evidence synthesis methods incorporating other data sources (see below). (Objective 1, 6, 7).

The capillary blood samples will be used to compare EIA signals between samples derived from DBS, venous plasma and capillary plasma samples as part of a proof-of-concept, methods development approach. The 100 sample size is based on the need for at least 10 positives, and is based on an assumed 10% seroprevalence. We will modify the number of capillary samples taken to ensure sufficient positive samples are available based on seroprevalence data.

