Sample size calculations for this study are challenging because of the lack of a gold standard test, and the fact that prevalence in the study population is both unknown and increasing over time. The following calculations assume that the HPA laboratory-based test is 100% sensitive and 100% specific, which is known not to be the case. The calculations are therefore no more than illustrative. We assumed that the true sensitivity and specificity of the HTK are both 98%. These are the minimum values currently considered acceptable by the MHRA (18/04/2020). The performance metric of the most interest is the PPV, defined as the probability that a person who tests positive does in fact have antibodies. Table 2 shows the expected 95% confidence intervals for sensitivity, specificity and PPV which would be obtained for a sample size of 1000 or 2500 participants, under various assumed values of prevalence in the study population. If we were to consider 90% PPV acceptable, and prevalence in the study sample was 20%, we would require 2,500 participants to obtain a 95% CI which was wholly above 90% PPV.

Evaluating Detection of SARS-CoV-2 antibodies using home test kits (EDSAB-HOME study)

Protocol 30.05.2020 Version 04.03

Table 2 The expected 95% confidence intervals (CIs) around estimated sensitivity, specificity and PPV under potential sample sizes of n = 1000 and n = 2500, assuming true sensitivity and specificity are both 98%.

	Study size	of n = 1000		Study size of	of n = 2500	
Prevalence in study population	Sensitivity 95% Cl	Specificity 95% CI	PPV in study population: estimate (95% CI)	Sensitivity 95% CI	Specificity 95% CI	PPV in study population: estimate (95% CI)
5%	0.93,1.00	0.97,0.99	0.72 (0.61,0.82)	0.95,1.00	0.97,0.99	0.72 (0.65,0.79)
10%	0.95,1.00	0.97,0.99	0.85 (0.78,0.91)	0.96,1.00	0.97,0.99	0.85 (0.80,0.89)
15%	0.95,1.00	0.97,0.99	0.90 (0.85,0.94)	0.96,0.99	0.97,0.99	0.90 (0.87,0.92)
20%	0.96,1.00	0.97,0.99	0.93 (0.89,0.96)	0.97,0.99	0.97,0.99	0.92 (0.90,0.95)
25%	0.96,1.00	0.97,0.99	0.94 (0.91,0.97)	0.97,0.99	0.97,0.99	0.94 (0.92,0.96)

Test performance may vary across populations, e.g. due to variation in underlying severity of disease. To allow exploration of this, initially we propose a cohort of 1500 healthcare workers and 1000 police officers, with later possible extension to the general public.

Analysis 1b

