We will also report test accuracy in comparison to locally relevant adaptations of the World Health Organisation [20th March, version 6] criteria for confirmed cases (RT-PCR positive), suspect cases (combining symptoms and exposure) and probable cases (suspect cases with inconclusive or no RT-PCR results).

Our adapted definition reflects UK screening and swabbing practice; see Appendix 2. On 5 March, the UK Government confirmed that local COVID-19 transmission was occurring. After this, it changed policy from a 'containment phase' based on active case finding and molecular screening of individuals meeting a definition based on WHO criteria to one of 'delay' in which testing was largely confined to hospitalised cases, based on limitations in testing capacity.

Our definition includes the WHO's recommended confirmed, suspect and probable cases. In addition, we are pre-specifying a category of 'symptoms but tested negative' because molecular testing may be insensitive.

Our approach will otherwise be similar to that in Analysis 1a.

Analysis 2

The key assumption of Analysis 1 (that the laboratory-based assay makes no errors) is known to be untrue. In Analysis 2, we will use the "known positive" status of up to 500 of the study participants, alongside additional data, to estimate the sensitivity and specificity of both the HTK and the laboratory-based assay.

Evaluating Detection of SARS-CoV-2 antibodies using home test kits (EDSAB-HOME study)

Protocol 30.05.2020 Version 04.03

Data from multiple sources, including the present study, will be synthesised together using a Bayesian latent class modelling / multi-parameter evidence synthesis approach.

As described on page 2, we propose additional data collection through two main routes. We will also attempt to identify as many other relevant data sources as possible. Relevant studies will be those involving the HPA assay, HPA and other assays including T-SPOT Coronavirus, HPA and the home test kit, and other assays which have been compared to HPA and the home test kit. Data from studies with each of these designs will improve estimation of the accuracy of both the HTK *and* the HPA assay. Attention will be focused on:

Other studies using two or more assays on populations with unknown prevalence. Information from studies with a wide range of different (unknown) seroprevalence values can contribute useful information about the sensitivity and specificity of the assays concerned.

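### The recruitment target is stated two ways, 2,500 workers plus up to 500 known positives or 2,500 including them, and the PPV argument for 2,500 suits only the first

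*Protocol*

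**What the plan says.** Four places in the protocol bear on the total.

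- **Recruitment.** Three key cohorts are listed: 1,500 healthcare workers, 1,000 police or other non-healthcare workers, and the general population, which is deferred. The text continues: "Additionally, a fourth cohort will be approached". This cohort consists of people who tested positive earlier in healthcare worker screening, and "We will attempt to recruit up to 500 such workers".
- **Three stages, stage one.** The known positives are counted within the total: the anticipated users, up to 500 known positives included, "are recruited (2,500 persons) prior to the HTKs becoming available".
- **Sample Size for Analysis 1 of Objective 1.** The figure 2,500 is justified by Table 2. With kit sensitivity and specificity of 98% and 20% prevalence in the study sample, 2,500 participants are said to give a 95% interval for PPV entirely above 90%. The section then states the make-up: "initially we propose a cohort of 1500 healthcare workers and 1000 police officers". Known positives are not mentioned.
- **Analysis 2.** The model uses the known-positive "status of up to 500 of the study participants, alongside additional data". This is compatible with either total.

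No place gives a figure that reconciles these statements. The 3,000 used below is the sum 1,500 + 1,000 + 500; the protocol does not print it.

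**The concern.** The same figure, 2,500, stands for two different samples. In the Recruitment and sample-size sections it is 2,500 workers, with known positives on top. In stage one it is as few as 2,000 workers plus up to 500 people chosen because they had tested positive.

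This matters because the protocol names PPV as the performance measure of most interest and rests 2,500 on a PPV interval at a given prevalence in the study sample. Known positives raise that prevalence by design. If they are counted, the 20% row of Table 2 can be reached through the recruitment mix while prevalence among the intended users is far lower. If they are not counted and 2,500 includes them, the number of workers behind the row is 2,000.

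**Working it through.** **Inputs.** Kit sensitivity and specificity are 98% each, with the laboratory reference assay (HPA) taken as perfect (sample-size section). Cohort sizes are as above. The share of known positives who are HPA-positive, s, is not given for this purpose. I assume 80-100%; the low end follows Appendix One, which puts detection of past disease at about 80%. Workplace prevalence is p.

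**Reproducing Table 2.** For N participants at prevalence p, expected true positives are 0.98pN, expected false positives are 0.02(1 − p)N, and PPV is their ratio TP/(TP + FP). At N = 2,500 and p = 20%:

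- TP = 0.98 × 500 = 490; FP = 0.02 × 2,000 = 40; PPV = 490/530 = 0.9245.
- Wald 95% interval: 0.9245 ± 1.96 × √(0.9245 × 0.0755/530) = 0.9245 ± 0.0225, or 0.902 to 0.947.

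The protocol prints 0.92 (0.90, 0.95). The other cells also reproduce to within about 0.01.

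**Pooled prevalence with 500 known positives inside 2,500.** Prevalence = (2,000p + 500s)/2,500.

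| Workplace prevalence | Pooled prevalence | Pooled PPV | PPV in workers alone |
|---|---|---|---|
| 0% | 16-20% | – | – |
| 5% | 20-24% | 0.925-0.939 | 0.721 |
| 10% | 24-28% | 0.939-0.950 | 0.845 |
| 20% | 32-36% | 0.958-0.965 | 0.925 |

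With all 500 recruited and pooled, the 5%, 10% and 15% rows of Table 2 could not occur. The 20% row would correspond to a workplace prevalence of only about 0-5%. With fewer known positives the floor falls: at 250 it is 250s/2,500, or 8-10%.

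**Pooled prevalence with 500 known positives on top (N = 3,000).** Prevalence = (2,500p + 500s)/3,000. The floor is 13-17%, and at p = 5% the range is 17.5-20.8%. Table 2 has no column for 3,000.

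**Workers only, at 20% prevalence.**

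- N = 2,500: 0.902 to 0.947, as above.
- N = 2,000: PPV = 392/424 = 0.9245, and 0.9245 ± 1.96 × √(0.9245 × 0.0755/424) = 0.899 to 0.950. This just misses the 90% criterion.
- The Wald lower limit reaches 0.90 at about 445.5 expected kit positives, from (1.96/0.02453)² × 0.06978. Kit positives are 0.98 × 0.20 + 0.02 × 0.80 = 0.212 of N, so N is about 2,100.

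**Specificity, at 10% workplace prevalence.** Half-width = 1.96 × √(0.98 × 0.02/n−). With 2,500 workers n− = 2,250, giving 0.58 percentage points. With 2,000 workers plus 500 known positives n− = 1,800 + 500(1 − s) = 1,800 to 1,900, giving 0.63 to 0.65 points.

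**The case against.** **The known positives may sit inside the 1,500 healthcare workers.** They come from healthcare worker screening, so they could be part of that cohort, reached by a second route. Stage one, the sample-size section and Analysis 2 would then agree on 2,500. But the Recruitment section calls them a fourth cohort, approached in addition to the others, which conflicts with this reading. It would also restore only the total: 2,000 unselected participants remain, and the pooled prevalences tabulated above still apply. Prevalence among the 1,500 healthcare workers would itself be at least 500s/1,500, or 27-33%.

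**The calculation is called illustrative, and 500 is a ceiling.** Both are true. The caveat concerns the imperfect reference assay, however, and does not say who is counted. The calculation is also the only justification given for 2,500. A smaller known-positive cohort shrinks the mismatch without removing it.

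**Reported PPV is not tied to the sample mix.** This largely stands. The Objective 1 text and Analysis 1a obtain PPV and NPV by Bayes' rule across a range of prevalences, Analysis 2 does so across pre-test probabilities, and results are tabulated by sub-population as well as pooled. A reader might infer that the final PPV would be misreported; the documents do not support that. The 0.72 against 0.92-0.94 contrast concerns how Table 2 is read, and any PPV quoted at the study's own prevalence.

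**The precision loss is very small.** This stands. Both worker-only intervals print as (0.90, 0.95). Wilson and exact lower limits are 0.899 even at 2,500, so the narrow miss at 2,000 depends as much on the interval method as on the 500 missing workers.

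**Conclusion.** The inconsistency is real and in the current text: the total is either 2,500 or up to 3,000, and the number of workers other than the known-positive cohort is 2,500 or as few as 2,000. The argument that 2,500 secures a PPV interval above 90% at 20% prevalence holds for the intended users only if the 2,500 are unselected workers. With 500 known positives inside the total, pooled prevalence is at least 16-20%, assuming 80-100% of them are HPA-positive. The 2,000 workers alone just miss the criterion (0.899 against 0.902, Wald).

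Three stronger conclusions might be drawn, and none is supported. Table 2 is not wrong; it reproduces. The study is not shown to be too small; the difference is in the third decimal place. Nor does it follow that known positives should count towards sensitivity only: Analysis 1a computes specificity over all HPA-negative samples, which can include a known positive, and Analysis 2 uses known-positive status to estimate both sensitivity and specificity. The point should be corrected because a planned size that the study relies on is stated in two incompatible ways, and correction costs very little.

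**What to change.** 1. Reconcile the Recruitment section, the stage one description and the sample-size section to one total, saying whether the up to 500 known positives are inside the 2,500 or on top of it.
2. State that the prevalence and PPV in Table 2, and any PPV quoted at the study's own prevalence, refer to the unselected workers without the known-positive cohort.
3. If 2,000 workers plus 500 known positives is meant, recompute the Table 2 block now headed n = 2,500 for n = 2,000. Restate the claim about the 90% PPV criterion, which at 20% prevalence becomes 0.899-0.950 by Wald.

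The cost is a few sentences and, in the third case, one recomputed block of the table with slightly less favourable precision. Analyses 1a and 2 need no change.
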